1.2 Secondary Objectives

Secondary aim 1: Assess the impact of MVPA across the RL, RH, and UC arms on cardiovascular fitness, quality of life, cognitive function and brain parameters related to AD (whole and regional brain volume, functional connectivity, cerebral blood flow) at baseline, 6, and 12 mos.

Secondary Aim 2: Determine the feasibility (retention, session attendance, use of recorded sessions (RH/RL only) and safety of RL, RH, and UC arms.

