burden (physical, emotional, financial). Caregiver stress will be assessed using the Caregiver Self-Assessment Questionnaire (CSAQ), which is a caregiving-specific measure of psychosocial stress and is an appropriate measure for depression screening⁷⁷. Caregiver quality of life will be assessed using the Adult Carer Quality of Life Questionnaire (AC-QoL)⁷⁸, which covers eight different domains for caregivers: support for caring; caring choice; caring stress; money matters; personal growth; sense of value; ability to care; and caregiver satisfaction.

Feasibility. Retention. Retention will be measured as the percentage of participants who complete the 12 mo. intervention, defined as completing the 12 mo. outcome assessments. Session attendance. Session attendance for both group MVPA and individual education/support sessions from baseline to 12 mos. will be obtained from records maintained by the health educator, and expressed as the percent of possible sessions. Attendance at group MVPA sessions will be defined as being logged in to the video conference and remaining on the screen for the entire 30-min session. Attendance at individual support/education sessions, for the both exercise and UC conditions, will be defined as answering the Zoom call, and being present on screen for the entire session. Use of recorded exercise sessions (RL and RH only) will be tracked using Dropbox which provides information on how many times each user watched a video. Safety. Safety will be measured by number of participants reporting a serious adverse event, i.e., any untoward medical occurrence that results in death, is life-threatening, requires inpatient hospitalization or results in persistent or significant disability/incapacity.

Descriptive outcomes. To characterize our study sample, we will measure weight, height and waist circumference in participants at baseline, 6, and 12 mos. Weight will be measured in light clothing on a calibrated scale (Model #PS6600, Belfour, Saukville, WI) to the nearest 0.1 kg. Standing height will be measured with a portable stadiometer (Model #IP0955, Invicta Plastics Limited, Leicester, UK). BMI will be calculated as weight (kg)/height (m²). Waist circumference will be assessed using the procedures described by Lohman et al.⁷⁹.

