7.1 Specification of Safety Parameters

Risks to the individual with AD and caregiver in this study are minimal. There have been no serious adverse events with PA interventions in any of our completed trials, including trials in adults with DS. Increased PA may be associated with minor injuries such as strains and sprains, and the potential for muscle soreness, particularly in the early stages of the PA protocol, may exist.

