7.2 Methods and Timing for Assessing, Recording, and Analyzing Safety Parameters

Staff involved in performance of the protocol will continually monitor participants for adverse events throughout all outcome's assessments, exercise sessions, and individual education session. All AEs and SAEs will be recorded in the studies REDCap database.

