Our second secondary aim will determine the feasibility (retention, session attendance, use of recorded sessions (RH/RL only), and safety) of RL, RH, and UC arms. We will estimate the proportion of participants retained, session attendance, use of recorded sessions and safety, i.e. significant adverse events across the 12 mo. trial, the proportion that adhere to treatment within each arm. Within the RL and RH arms, 32 participants allow us to estimate these proportions with a margin of error no greater than 0.09. Within the UC group, 16 participants will allow us to estimate these proportions with a margin of error no greater than 0.125.

For all analysis we will explore the impact of demographic characteristics such as gender, and racial/ethnic subgroups.

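### The planned safety outcome counts only serious adverse events, so as specified it does not describe by arm the non-serious injuries that the protocol names as the expected harms

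*Combined protocol and SAP*

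**What the plan says.** Section 1.2 makes safety by arm part of Secondary Aim 2: "Determine the feasibility (retention, session attendance, use of recorded sessions (RH/RL only) and safety of RL, RH, and UC arms".

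The Feasibility paragraph of section 5 defines the outcome: "Safety will be measured by number of participants reporting a serious adverse event". It lists death, life-threatening events, inpatient hospitalization and lasting disability, and sets no condition that the event be related to the intervention.

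Section 8.3 plans proportions within each arm, but describes the safety item differently: "use of recorded sessions and safety, i.e. significant adverse events across the 12 mo. trial". The word *significant* is not defined there or elsewhere.

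Section 7.1 reports the team's experience: "There have been no serious adverse events with PA interventions in any of our completed trials, including trials in adults with DS". It then names the expected risks: "Increased PA may be associated with minor injuries such as strains and sprains, and the potential for muscle soreness".

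Section 7.2 states that "All AEs and SAEs will be recorded in the studies REDCap database". Its title includes the analysis of safety parameters, but its text describes none. Section 7.3 excludes light soreness of muscles or joints from the definition of an adverse event. Section 7.4 sends adverse events to the DSMB twice a year and a summary to the IRB annually, with no by-arm summary mentioned.

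**The concern.** The harms that the protocol expects and the harms that it plans to report are different sets. A strain or sprain that does not lead to hospitalization or lasting disability is entered in the database but reaches no planned safety estimate.

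This matters because RL and RH, if successful, are to be carried into a later trial (sections 5 and 8.1.1), and they differ only in group-session frequency, one against three per week. The designers of that trial will want to know how many participants in each arm were injured. A table with few or no serious events could be read as showing that the programme is safe, although it holds no information on strains and sprains at any injury rate. Choosing non-serious categories after the data are in is also weaker than naming them now.

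**Working it through.** **The plan's own figures.** Section 8.3 gives margins of error for proportions of 0.09 (n = 32) and 0.125 (n = 16), with no confidence level. They reproduce as one standard error at p = 0.5:

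- n = 32: √(0.25/32) = 0.088
- n = 16: √(0.25/16) = 0.125

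The corresponding 95% half-widths are 1.96 × 0.0884 = 0.173 and 1.96 × 0.125 = 0.245. So the stated margins understate the 95% uncertainty, and they are not a useful guide for events near zero. Exact binomial limits are used below.

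**Inputs.** Arm sizes are 32 (RH), 32 (RL) and 16 (UC), from section 8.1. The documents give no serious-event risk. Section 7.1 reports none with physical-activity interventions in completed trials, but gives no denominator or follow-up time. The risks below are assumptions, spread widely for that reason.

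**Chance of no serious event in an arm:** (1 − p)ⁿ.

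| Assumed 12-month risk p | n = 32 | n = 16 |
|---|---|---|
| 0.5% | 85% | 92% |
| 1% | 72% | 85% |
| 2% | 52% | 72% |
| 5% | 19% | 44% |
| 10% | 3% | 19% |

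**What zero events would establish.** The exact two-sided 95% upper bound is 1 − 0.025^(1/n):

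- 0/32: 1 − 0.025^(1/32) = 10.9%
- 0/16: 1 − 0.025^(1/16) = 20.6%

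**What an added adverse-event proportion would give.** Exact (Clopper–Pearson) 95% intervals at assumed counts of roughly 10%, 20% and 30%:

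| n | Count | 95% interval |
|---|---|---|
| 32 | 3 | 2.0% to 25.0% |
| 32 | 6 | 7.2% to 36.4% |
| 32 | 10 | 16.1% to 50.0% |
| 16 | 2 | 1.6% to 38.3% |
| 16 | 3 | 4.0% to 45.6% |
| 16 | 5 | 11.0% to 58.7% |

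These are wide, but they describe the harm that section 7.1 names.

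**Occasions to report.** Section 6.2.4 says participants are asked about adverse events at group and individual sessions. With two individual sessions a month (Table 1), and weekly sessions converted by 52/12, the scheduled contacts per month are:

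- RH: 3 × 52/12 + 2 = 15
- RL: 52/12 + 2 = 6.3
- UC: 2

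The narrative of section 3 gives individual sessions weekly for RL and RH and monthly for UC. On that reading the contacts are 17.3, 8.7 and 1, in the same order. The schedule in section 6.1 also marks adverse events in a daily column, but section 6.2.4 describes no daily enquiry.

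**The case against.** The strongest reply is that nothing is lost. Every adverse event goes into REDCap, allocation is stored there too (section 8.1.1), and the DSMB reviews events twice a year. This is also an early-stage, descriptive trial with no safety hypothesis. That is right as far as it goes. A reader might infer that the trial *cannot* describe minor injuries by arm, and the documents do not support that: the table could be made, but it is not planned. DSMB review is oversight, and does not supply a trial result for Secondary Aim 2.

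A reader might also infer that the serious-event table is bound to be empty. It is not. Section 7.1 speaks of events with physical-activity interventions in the team's own completed trials, whereas the section 5 outcome counts serious events of any cause, so an unrelated hospitalization would count. The first table shows how far the chance of an empty arm depends on the assumed risk.

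It can be said that a sprain that stops someone exercising already lowers attendance, and perhaps retention, both of which are estimated by arm. This is true, but neither measure identifies injury as the cause.

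Finally, minor injuries would not separate the arms well either. Even a doubled rate, 8/32 (11% to 43%) against 4/32 (4% to 29%), gives overlapping intervals, and the unequal contacts confound any comparison. That stands, and it limits the added estimates to within-arm description.

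**Conclusion.** The point holds as a mismatch between the safety aim, the named risks and the planned estimate. As written, Secondary Aim 2 would report serious events only, or an undefined class of *significant* events, and would leave the expected strains and sprains unreported by arm although they are recorded. The gap lies in the outcome definition and the analysis plan; data collection falls short only for light soreness, which section 7.3 excludes.

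The mismatch itself follows from the text and needs no assumed rate. How little the serious-event count would say does depend on the assumed risk. It would be tempting to claim that adding minor injuries would show whether three sessions a week cause more harm than one; the arm sizes and the unequal ascertainment do not allow that. This is an inexpensive improvement that should be made, and it does not threaten the primary aim.

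**What to change.** In the Feasibility paragraph of section 5 and in section 8.3:

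1. Keep the count of participants with a serious adverse event.
2. Replace *significant* with *serious* in section 8.3, or define it.
3. Add, for each arm, the number and proportion of participants with (a) at least one adverse event and (b) at least one musculoskeletal injury, each with an exact 95% interval.
4. Report withdrawals or missed sessions due to an adverse event only where the reason is recorded. Attendance is kept as a percentage of possible sessions, and the only stated collection of reasons for missed sessions is the exit interview in a 20% sample.
5. State that light soreness is not captured.
6. State that participants are asked at sessions, so RH has more occasions to report than RL, and RL more than UC. Present the new estimates as within-arm description, and do not read differences between arms as an effect of session frequency.

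The cost is wording in two places and a few table rows. Item (a) uses data already recorded. Item (b) needs a simple rule for classifying events from the Adverse Event Form, which the documents do not describe and which should be written before the data are examined.

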5.1 Adherence Assessment

Retention. Retention will be measured as the percentage of participants who complete the 12 mo. intervention, defined as completing the 12 mo. outcome assessments. Session attendance. Session attendance for both group MVPA and individual education/support sessions from baseline to 12 mos. will be obtained from records maintained by the health educator, and expressed as the percent of possible sessions. Attendance at group MVPA sessions will be defined as being logged in to the video conference and remaining on the screen for the entire 30-min session. Attendance at individual support/education sessions, for the both exercise and UC conditions, will be defined as answering the Zoom call, and being present on screen for the entire session. Use of recorded

exercise sessions (RL and RH only) will be tracked using Dropbox which provides information on how many times each user watched a video.

6 STUDY PROCEDURES

6.1 Schedule of Evaluations

| Assessment | Home Screening: Visit-1 (Day-30 to Day -1) | Enrollment, Randomization: KUMC Visit 1 (Day -14 to Day -1) | Start of Exercise Intervention (Day 0) | KUMC Visits | | | | At- Home Activities | | |
|---|--|---|--|--|------------------------|--|-------------------------|---------------------|-------------|-------|
| | | | | Accelerometer Mailed to Home (Month 3) | KUMC Visit 2 (Month 6) | Accelerometer Mailed to Home (Month 9) | KUMC Visit 3 (Month 12) | Weekly | Bi- Monthly | Daily |
| Informed Consent Form | X | | | | | | | | | |
| Demographics | X | | | | | | | | | |
| Medical History | X | | | | | | | | | |
| DSQIDD | X | | | | | | | | | |
| Enrollment/Randomization | | X | | | | | | | | |
| Current Medications | | X | | | X | | X | | | |
| MVPA | | X | | X | X | X | X | | | |
| Cardiovascular Fitness | | X | | | X | | X | | | |
| Cognitive Function Test | | X | | | X | | X | | | |
| Quality of Life Questionnaire | | X | | | X | | X | | | |
| Anthropometrics | | X | | | X | | X | | | |
| Physical Function | | X | | | X | | X | | | |
| Caregiver Outcomes | | X | | | X | | X | | | |
| Optional practice session and MRI | | X | | | X | | X | | | |
| Exercise Session Attendance | | | | | | | | X | | |
| Individual Education Session Attendance | | | | | | | | | X | |
| Fitbit | | | | | | | | | | X |
| Adverse Events | | X | | | X | | | X | X | X |

6.2 Description of Evaluations

6.2.1 Screening Evaluation

These evaluations occur to determine if the candidate is eligible for the study.

Consenting Procedure

Remote video chat sessions (Zoom) or in person consent meetings depending on participant preference, will be scheduled with participants, caregivers, and their legal guardian (if applicable) deemed to be initially eligible to describe the project in detail, answer questions, verify eligibility, and to obtain participant consent or, if the participant is not their own legal guardian, guardian consent and participant assent.

For remote video chat sessions (Zoom): Prior to the consenting session, the participant will be sent the consent form and cover letter through Kansas University Medical Center's (KUMC) secure email system. Study staff will set up a virtual Zoom meeting that allows for remote video chat. Study staff will “share screen” the consent document and walk through each section, noting questions that arise, and answer these questions fully. The signed and dated consent form will be submitted online through REDCap.

For in person consent meetings: study staff will meet at a mutually chosen location to meet with the potential participant, study partner, and legal guardian (if applicable). They will review the study with them, read the informed consent to them, and answer any questions. The participant will be allowed to keep the consent form and read over on their own and join at a later time. We will collect informed consent from participants, or if a participant is not their own legal guardian, we will collect participant assent and legal guardian/surrogate decision maker consent. We will obtain assent away from family members to make sure participants don't feel like they have to be in the study.

Screening

After consent, participant will be asked to complete the DSQIDD to verify eligibility. This will take place at the consenting appointment within 1 month of starting the study.

6.2.2 Enrollment, Baseline, and/or Randomization

Enrollment

Enrollment is defined as the date in which a participant has signed a consent form, passes the DSQIDD turned in a physician consent form.

Baseline Assessments.

Baseline Assessments will take place within two weeks of starting the intervention and will include

- Medication review
- MVPA using accelerometer
- Cognitive Function
- Cardiovascular Fitness
- Quality of Life Questionnaire
- Anthropometrics
- Physical Function (Sub-sample).

- Caregiver Outcomes (Sub-sample).
- Optional practice MRI
- MRI (Sub-sample).
- Adverse Events Review

Randomization

Randomization will take place within 2 weeks before the start the intervention.

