Orientation. Each participant and their study partner will be asked to attend a group orientation session (~60 min.) conducted at the University of Kansas Medical center and led by their health educator. In addition to describing study requirements and distributing iPads, Fitbits, resistance bands, etc., this meeting is designed to establish rapport between the health educator and participants, and between participants themselves, prior to initiating the group video conference sessions. The health educator will describe and demonstrate the ZoomTM software and the Fitbit and will allow time for practice and questions. Additionally, basic stretching exercises, the use of the resistance bands, and simple dance movements will be demonstrated and practiced.

Group sessions-schedule. Group exercise sessions will be scheduled between 10 a.m. and 7 p.m., 3 days/wk. for RH and 1 day/wk. for RL. This time window was selected based on the preference of participants in our 12-wk pilot trial in individuals with DS. Prompts reminding participants of upcoming sessions will be sent via the iPad. The same health educator will conduct MVPA sessions for both the RH and RL groups in each cohort to minimize health educator effects.

Group sessions-Delivery. All MVPA sessions will be conducted by a health educator experienced in working with individuals with DS and supervised by [name]. Group sessions will be delivered using an iPad tablet computer provided to all participants. The iPad will be pre-loaded with video-conferencing software (ZoomTM) which allows participation by multiple users. Participants will be provided with an iPad/HDMI adaptor, which allows video conference sessions to be displayed on a larger TV screen, if desired. Tutorials describing trouble shooting for common technical problems, e.g., internet connectivity etc., will be loaded on the iPad. Participants with technical issues during the intervention can also contact research staff by phone or email. Access to non-study related materials, e.g., web browsing, app store, etc., will be blocked on all iPads. The iPads for both groups will also be pre-loaded with the Fitbit application.

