Schedule. MVPA will be assessed at baseline, 3, 6, 9, and, 12 mos. Equipment. MVPA will be assessed using an ActiGraph (ActiGraph wGT3XBT, ActiGraph LLC, Pensacola, FL) tri-axial accelerometer (3.3 x 4.6 x 3.5 cm, wt. = 19 g., dynamic range \pm 8 g). The ActiGraph provides valid and reliable assessments of physical activity in adults ¹³⁻¹⁵, and has been widely used to describe physical activity levels in adults with DS ¹⁶⁻¹⁸. Our group has used the ActiGraph in previous trials in adults with IDD ⁴, and in typically developing adults ^{19, 20}. We have also developed a custom program for processing ActiGraph data, using protocols described subsequently. Protocol. There is a lack of consensus on the best protocols to collect, process, and score ActiGraph data ²¹⁻²⁴. Thus, our decisions regarding ActiGraph location, monitoring period, data processing, etc. were based on current practice, as described below. Participants will be asked to wear the ActiGraph on a belt over the non-dominant hip at the anterior axillary line during waking hours for 7 consecutive days, with the exception of bathing, swimming, and contact sports. A 7-day monitoring period provides a reliable estimate of MVPA ^{22, 25, 26}. The hip rather than the wrist location will be used due to the lack of comparable data, and established protocols for assessment of MVPA using wrist-worn ActiGraphs ²⁷⁻²⁹. ActiGraph distribution/reminders. Research staff will distribute and demonstrate proper placement of the ActiGraphs at laboratory visits scheduled at baseline 6, and 12 mos. ActiGraphs will be distributed by mail for the 3, 9 mo. assessments. ActiGraphs will be returned by postage paid mail following completion of all assessments. Daily reminders to comply with the ActiGraph protocol will be sent to participants' iPads each morning during the 7-day monitoring period. We have employed similar distribution and reminder protocols in previous trials ^{4, 6, 20, 30, 31}. Our current supply of ActiGraphs, plus the additional units requested in this proposal, will allow assessments to be completed on all participants in the proposed timeframe. Data collection. ActiGraphs will be initialized and downloaded using ActiLife Software version 6.13.3 or higher (ActiGraph Corp, Pensacola, FL) and set to collect in the raw data mode from all 3 axes at 60 Hz. Although the wGT3XBT collects raw data from 3 axes, results from studies assessing the benefit of 3 axes vs 1 axis (vertical) are conflicting ³²⁻³⁴. In addition, there are currently no established algorithms for using either the raw data or the vector magnitude (square root of the sum of the squares of each of the 3 axes) to estimate MVPA ^{35, 36}. The widely used cut-points for determining activity intensity in adults ³⁷ proposed for this trial use acceleration data from the ActiGraph vertical axis. However, raw data from all 3 axes will be downloaded and stored; and will be available should algorithms for processing this data become available during the course of this trial. Data processing. Accelerometer data will be processed using the protocol for adults used in the 2003-2004 and 2005-2006 cycles of NHANES ^{37, 38}. Data will be aggregated over 60-sec epochs. The following intensity cut-points will be used: sedentary (< 1.0 MET; \leq 100 counts/min), light (1.1-2.99 METs; 101-2019 counts/min.), moderate (3.0-5.99 METs; 2020-5988 counts/min) and vigorous \geq 6 METs; \geq 5999 counts/min) ^{37, 38}. Non-wear time will be defined as at least 60 consecutive minutes of zero counts, with allowance for 1-2 min. of counts between 0 and 100. Counts \geq 20,000/min will be considered spurious ³⁹. All accelerometer data processing will be completed using custom SAS/R programs developed by our team.

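### As scheduled, the 7-day baseline MVPA week can follow disclosure of allocation and run past Day 0

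*Combined protocol and SAP*

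**What the plan says.** - **Timing of randomization.** Section 6.2.2 states: "Randomization will take place within 2 weeks before the start the intervention".
- **Timing of baseline.** The same section states: "Baseline Assessments will take place within two weeks of starting the intervention and will include", and the list that follows includes accelerometer MVPA. It does not say which of the two comes first.
- **Schedule.** In Section 6.1 both items are marked in the column headed "Enrollment, Randomization: KUMC Visit 1 (Day -14 to Day -1".
- **Device issue and wear.** Section 5 (Primary Outcome- MVPA) states: "Research staff will distribute and demonstrate proper placement of the ActiGraphs at laboratory visits scheduled at baseline 6, and 12 mos". The device is worn "during waking hours for 7 consecutive days". Return is by post: "ActiGraphs will be returned by postage paid mail following completion of all assessments".
- **Reminders.** "Daily reminders to comply with the ActiGraph protocol will be sent to participants' iPads each morning during the 7-day monitoring period". The Orientation paragraphs of Section 5 are where participants receive those iPads: "In addition to describing study requirements and distributing iPads, Fitbits, resistance bands, etc".
- **Blinding.** Section 8.1.1 says participants are not blinded to their arm.
- **Analysis.** Section 8.3 summarises MVPA change from baseline at each visit, fits a mixed model to that change across the three arms, and correlates change in MVPA with change in the secondary outcomes.

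**The concern.** A device handed over at Visit 1 and worn for a week cannot yield a completed baseline at Visit 1. If randomization takes place at that visit, the whole baseline week follows it. No section makes disclosure of allocation, orientation, Fitbit issue or Day 0 wait for the wear week to end.

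The reminder arrangement points the same way. Section 5 makes no exception for the baseline week, so reminders on the study iPad require the iPad to be in hand. It is given out with the Fitbit at an orientation that is described separately, with different content, for RL/RH and for UC. That orientation presupposes allocation.

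At stake is the reference value for the trial's main product, the effect sizes for change in MVPA that are meant to inform a later trial. If part of the baseline week falls after Day 0, the arms differ in exposure during it: three group sessions a week in RH, one in RL, none in UC. A baseline week worn too late cannot be collected again.

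**Working it through.** **1. The plan's own figure.** Section 8.1 claims 99%, 98%, 94% and 89% confidence of estimating an arm mean within ±5 min, with SD 10 and n = 32, 24, 16 and 12. Confidence = 2·T(5 / (10/√n)) − 1, where T is the t distribution function with n − 1 degrees of freedom. This gives 99.2%, 97.8%, 93.6% and 88.9%, so the figures reproduce. They concern arm means at single time points and say nothing about the timing of baseline.

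**2. Overlap with Day 0.** Let v be the visit day, from −14 to −1. If wear starts on the visit day it covers v to v+6, and the overlap is max(0, v+7). If wear starts the next day it covers v+1 to v+7, and the overlap is max(0, v+8).

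| Visit day | Days on or after Day 0, wear from visit day | Days on or after Day 0, wear from next day |
|---|---|---|
| −14 to −8 | 0 | 0 |
| −7 | 0 | 1 |
| −6 | 1 | 2 |
| −5 | 2 | 3 |
| −4 | 3 | 4 |
| −3 | 4 | 5 |
| −2 | 5 | 6 |
| −1 | 6 | 7 |
| Permitted visit days with overlap | 6 of 14 | 7 of 14 |
| Mean if visits are uniform (assumption) | 21/14 = 1.5 | 28/14 = 2.0 |

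Wear that ends before Day 0 needs a visit by Day −7 (wear from the visit day) or Day −8 (wear from the next day). The permitted window runs to Day −1.

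**3. Illustrative size.** Inputs: potential session MVPA of 90 min/wk in RH and 30 in RL (Section 5, Homework assignments), none in UC, and SD about 10 min (Section 8.1). Assumptions: sessions are spread evenly over the week, visit days are uniform, and a share f of potential session MVPA is reached in week 1, with f from 0.25 to 1. Low f is more plausible because Section 5 describes the first sessions as light-to-moderate until about 6 weeks.

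Baseline shift = f × (weekly session MVPA / 7) × (overlap days / 7).

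- RH, wear from next day: 90/7 × 2/7 = 3.7 min/day at f = 1, and 0.9 at f = 0.25.
- RL, wear from next day: 30/7 × 2/7 = 1.2 at f = 1, and 0.3 at f = 0.25.
- RH, wear from visit day: 90/7 × 1.5/7 = 2.8 at f = 1, and 0.7 at f = 0.25.
- One RH participant with all 7 days after Day 0: 12.9 at f = 1, and 3.2 at f = 0.25.

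For scale, the standard error of an RH−UC difference in means is 10 × √(1/32 + 1/16) = 3.1 min.

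**4. Knowledge of allocation.** The documents give nothing from which to compute this. Each 1 min/day of differential reaction moves an effect size by 1/10 = 0.1 SD, in either direction.

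**The case against.** The strongest reply is that a missing order is not a wrong order. The Visit 1 column is a 14-day window and need not be a single appointment. Section 6.2.2 lists baseline assessments before randomization. Sections 5 and 8.1.1 describe cohorts of about 10 to 20, randomized by the statistician, with envelopes passed to the coordinator. That is compatible with allocating after the devices come back. Section 5 also has assessment staff blinded, which fits poorly with revealing the arm at the visit (Section 8.1.1 conflicts on staff blinding). If the assessment means the full week of measurement, wear past Day −1 is already outside the schedule. All of this stands, so a reader who infers that randomization is planned before baseline wear goes further than the documents do.

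Three further limits also stand:

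- Fitbits, iPads, resistance bands and an orientation go to all three arms. Reaction to them would lower measured change in every arm but should largely cancel between arms.
- The model in Section 8.3 has no baseline covariate, so a warning against adjusting for this baseline does not bear on the stated analysis.
- Posting the baseline device, as at months 3 and 9, would lose the in-person demonstration.

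What the reply does not supply is a rule. The visit window and the issue of the device at the visit, both followed exactly, still permit a baseline week after disclosure or after Day 0.

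**Conclusion.** The point holds as a gap in sequencing that should be fixed. It is not evidence that any baseline is contaminated. It affects MVPA change from baseline in Section 8.3 and the correlations with MVPA change.

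A reader might extend it to every change-from-baseline outcome. The documents do not support that: fitness, cognition, quality of life and imaging are measured at the visit and are less exposed, and raw follow-up means of MVPA do not use baseline.

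Early-session overlap would pull the RH and RL contrasts with UC toward zero. Reaction to knowing the arm could go either way, so the net direction is not certain.

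Under the assumptions shown (uniform visits, wear from the next day, f from 0.25 to 1), the average RH shift is about 0.9 to 3.7 min/day, or 0.09 to 0.37 SD. The low end is more plausible and is under a third of the RH−UC standard error. It would still be a systematic error in an effect size meant for planning the next trial. A reader might also infer that overlap cancels 29% of a session-driven effect. That figure is only 2/7, and it requires week-1 session MVPA to equal the full later effect, which the light-to-moderate early sessions contradict.

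**What to change.** In Sections 6.1 and 6.2.2:

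- Take randomization out of the KUMC Visit 1 column and make it a separate, later step.
- Hold Visit 1 no later than about Day −8, or earlier if allocation and orientation need time before Day 0. Keep the in-person issue and demonstration of the ActiGraph.
- Require the 7-day baseline wear to be complete before allocation is disclosed, before orientation and Fitbit issue, and before Day 0.

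In Section 5, send baseline-week reminders by phone, text or the study partner, since the study iPad would not yet have been issued.

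The cost is a narrower baseline-visit window in each cohort and a different reminder route for one week. No participants or measurements are added.
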